However the most of the literature on the use of changes in the ONSD for monitoring the changes in ICP came from the patients in the intensive care units with elevated intracranial pressure.^{2,7} Currently there are no data on how ONSD changes with acute increase or decrease in ICP. In addition, we don't know how soon the ONSD changes with acute changes in intracranial pressure.

Intracranial pressure is determined by the intracranial volume which in turn determined by the intracranial content namely, brain tissue, intracranial vessels (artery and veins) and the cerebrospinal fluid. There are limited non-surgical options that can be used to alter the ICP. Increase in the volume of intracranial vessels by either arterial dilation and/or occlusion of venous drainage can lead to increase in intracranial pressure. Carbon dioxide (CO₂) is a potent cerebral vasodilator, hypercapnia induced cerebral vasodilatation can lead to increase in ICP secondary to increase in intracranial volume. Similarly, obstruction to the cerebral venous drainage can also increase the intracranial pressure. Controlling the CO₂ and improving the venous drainage are the two fundamental principles in the anesthesia management of patients with increased ICP.^{6 8}

In order to use transorbital ultrasonographic measurement of ONSD as a method of monitoring changes in ICP, we need to determine how reliable the change in ONSD with controlled acute changes in intracranial pressure is. Controlled changes in ICP can be produced by either manipulation PCO₂ and/or cerebral venous

drainage. Among the methods available for CO₂ manipulation, we have shown that Model-based Prospective End-Tidal Targeting (MPET) system (RespirAct™-Thornhill research Inc) is the most reliable method for accurate and precise targeting of CO₂.⁹⁻¹⁰ Briefly, the RespirAct™ is a custom designed breathing circuit that uses computer controlled gas blending to quickly and precisely control end-tidal carbon dioxide levels⁹. The RespirAct™ has two main features for this study. First, it is capable of rapidly and precisely targeting a series of PetCO₂ independent of the subject's breathing pattern¹⁰. These changes can be induced within three breaths, are accurate to within ± 1 mmHg, and can be sustained at constant levels. Second, it has been shown in humans and animals that a unique characteristic of this system is that the end tidal CO₂ (PetCO₂) is precisely equal to arterial CO₂ (PaCO₂).⁹ With regards to venous outflow obstruction, both Valsalva maneuver (forced inspiration with closed glottis) and /or compression of internal jugular veins (IJV) are the two commonly used physiological methods that can cause an increase in ICP. However, compared to Valsalva maneuver which is dependent on the individual's effort and a variable effect, jugular venous compression is more reliable and reproducible method to increase ICP. Bilateral jugular occlusion is sometimes used during neurosurgical procedures during craniotomy opening especially in patients who are at risk of air embolism.⁽¹¹⁾ Jugular venous occlusion can be done using a custom made neck collar and previous investigations have used a similar device in a rat model to demonstrate the protective effects on slosh-mediated brain injury by increasing intracranial blood volume^{12,13}. While the collars have not yet been studied on people for their effectiveness at preventing

concussions, many studies have looked at the effect of neck collars on both jugular compression and ICP.^{14,15}

Aim of our study to determine the changes in ONSD with acute controlled changes in ICP in healthy volunteers. Transorbital ultrasound will be used for measuring the changes in ONSD. The controlled changes in ICP will be produced by manipulating the PCO₂ with the use of Respiract and jugular venous compression with the use of custom made neck collar.

References

References

1. Lundberg N. Continuous recording and control of ventricular fluid pressure in neurosurgical practice. *Acta Psychiatr Scand Suppl* 1960;36(149):1-193.


Hypothesis

Our hypothesis is that there will be a change in *optic nerve sheath diameter (ONSD) with the raised PCO₂ and internal jugular venous occlusion*

Objective of study

The main objective of this study is to determine the changes in ONSD with controlled increase in intracranial pressure with hypercapnia and jugular venous occlusion in healthy human volunteers.

Proposed Methodology

The study will be conducted in accordance with guidelines set forth by the University of Toronto, University Health Network Ethics Committee for use of human subjects in research. Ethics board approval will be obtained as well as written consent from each subject.

Study Design

This will be a prospective, non-randomized, observational study.

Recruitment

Healthy volunteers will be recruited by poster advertisement around the hospital. They will be asked to contact [name], Research coordinator for the study. His contact number and email will be provided. They will then be screened according to the inclusion and exclusion criteria's to see if they are suitable for the study.

Inclusion criteria

Adult healthy volunteers who are above the age of 18

ASA 1

Body mass index (BMI) less than and equal to 35

Neurologically normal subjects with no symptoms other than occasional non-severe headache

Exclusion criteria

BMI above 35

Lack of informed consent

Language barrier

Medical students and/or anesthesia residents going through the department as part of their rotation

Pregnancy

Frequent migraine headache

Informed Consent

The background of the study, benefits and risks will be explained to the subject and the informed consent form will be signed and witnessed if the subject agrees to participate.

Study protocol

Ultrasound measurement of ONSD

All volunteers will be fully awake throughout the study and be kept comfortable. The transocular ultrasound examinations of the ONSD will be carried out using a SonoSite Edge (FUJI FILM SonoSite Inc. US) ultrasound system and a 7-10 MHz linear probe. Two trained investigators will perform investigations on both eyes of all subjects independently without being aware of each other's study results. All patients will be in the supine position and the probe will be gently placed on the temporal part of the closed upper eyelid. Contact with the eye will be gentle at all times and pressure never directly applied on the globe with the probe. A Tegaderm film (Transparent film dressing, 3M Canada) will be applied over the eye to protect the patient from the ultrasound gel applied during sonography. Once the anterior part of the optic nerve is depicted in the transverse/axial plane showing the papilla and optic nerve in its longitudinal course, the ONSD will be assessed 3 mm behind the papilla, as described previously (Figure 3). Each eye will be examined 3 times by each investigator and the mean value of the ONSD will be used for further calculations.

Carbon dioxide Manipulation

The volunteers will don an airtight mask connected to the RespirAct™ sequential gas delivery breathing circuit. The subject will lie supine on a stretcher. Gas will be supplied by a computerized MPET system (RespirAct™). During control conditions, room air will be supplied at flows greater than the subject's minute ventilation. These studies will be done at the subject's baseline end-tidal CO₂ tension (usual range 35 – 40 mmHg). The PetO₂ will be fixed at 100 mmHg, a normal PETO₂ for most subjects. We will record baseline values for 120 seconds and then the PetCO₂ will be increased to +10 mmHg (Hypercapnia I) from baseline and held for 5 minutes in order to complete ONSD measurements. The venous compression neck collar will then be applied and ONSD measurements will be repeated. Following measurements, the PetCO₂ will be returned back to baseline (Figure 1). This sequence will again be repeated increasing the PetCO₂ to +15 mmHg (Hypercapnia II) from baseline before returning to baseline. The subject will then have PetCO₂ decreased to -10 mmHg (Hypocapnia) from baseline before returning to normal capnia. The study will stop at this point. During each cycle, the PetO₂ and PetCO₂ will be controlled by delivering mixes of source gases consisting of O₂, air, and blends of CO₂, N₂ and O₂. The speed and accuracy of the RespirAct™ for modulating PetCO₂ while maintaining constant PetO₂ is shown in Figure 2.

The RespirAct™ system has been used extensively in more than 15 UHN studies. Over 500 spontaneously breathing human subjects have been studied under these approved protocols. Results have been published in abstract and peer reviewed form and a number of Master's and Doctorate Theses at the University of Toronto ([name], [name], [name], [name], [name], [name], [name]). The RespirAct™ is still considered an

investigational device and Health Canada approval will be obtained before beginning the study.

Internal jugular compression using a Neck collar

A custom made collar consisting of two (2 x 3 x 1.5 cm) soft gauze pledgets held over the IJV by an elastic retainer will be applied around the patient's neck which can be adjusted to the subject's neck circumference using Velcro.(Velcro, US) This will apply only minimal pressure on the neck, which is comparable to wearing a tight dress shirt. In order to confirm the jugular venous occlusion with the neck collar, we will measure the diameter and flow in the IJV using the ultrasound in each subject in both sitting and supine positions with and without collar. Similarly to determine the lowest pressure needed to occlude the IJV, a 100 ml fluid (normal saline) bag which is attached to a pressure manometer will be placed on the subjects' neck below the collar and the minimal pressure at which there is complete occlusion of IJV will be recorded. The venous compression neck collar will be applied at each CO₂ levels (normocapnia, Hypercapnia I and II and hypocapnia) and ONSD measurements will be measures before and after the collar.

Risks

1. Carbon dioxide

The physiologic stresses of CO₂ manipulation on this proposal can be considered minimal. The higher PetCO₂ required will not exceed 60 mmHg nor will this change be sustained for long (10 minute intervals). The lower level of PetCO₂ is frequently seen with exercise. This range of PetCO₂ is physiological and is experienced repeatedly by most people over a regular day. Hyperventilation with hypocapnic PetCO₂ is common in day-to-day living (anger, excitement, running). Taking sedatives (alcohol) or even normal sleep can be associated with a PCO₂ of ~ 50 mmHg.

2. RespirAct™

The inhaled gases used in this study are supplied by a computerized MPET system. During control conditions, room air will be supplied at flow greater than the subject's minute ventilation. The subject will be monitored continuously for heart rate, depth of sedation and saturation by pulse oximetry by an attending physician (neurosurgery/ICU or anesthesia). When there is any concern about the subject's condition an alarm button on the RespirAct™ will deliver 100% oxygen to the subject as an extra safety feature. The re-breathing circuit can be easily removed from the subject's face.

Theoretically, CO₂ manipulation can cause further impairment of perfusion in areas with low flow and poor reactivity, by a "steal phenomenon" – flow would be diverted to areas of preserved reactivity during stimulation. In spite of this theoretical possibility this seems to be exceedingly uncommon even in patients with

severe chronic ischemic conditions such as Moyamoya, where the cerebrovascular reactivity is frequently tested with CO₂ manipulation and acetazolamide, and more recently at the Toronto Western Hospital, using the RespirAct™ (several protocols are currently approved by the UHN REB). As well, it is anticipated that the majority of our subjects studied will be young and otherwise healthy.

The device has built in safety features and alarms. For example,

- All source gases contain at least 6 % oxygen to limit the level of hypoxia to a safe and asymptomatic level in case of an error or technical problem with implementing the desired blend of gases
- The blender has a “dead man’s switch” that defaults to 100% oxygen at 12 L/min if there is any loss of communication between the blender and the computer such as “hanging up” of the software or computer, loss of power to computer or blender, any one of a series of pre-set alarm conditions are met.
- The RespirAct™ has a large red button that if pushed switches the gasses to 100% oxygen allowing fast and easy intervention in case of any problematic issue.
- The gas delivery circuit has a rubber button with a handle accessible to the subject that if pulled immediately opens the circuit and provides the subject with room air.
- In addition to being monitored by a physician, the RespirAct™ continuously assesses a series of subject and hardware parameters to assure that they stay within pre-set safe limits. Some of these are:
 - Subject parameters:
 - Respiratory rate
 - Peak expired CO₂ concentration
 - inspired CO₂ concentration
 - expired O₂ concentration
 - inspired O₂ concentration
 - apnea time
 - Blender parameters
 - Delivered flow of each gas is equal to the demanded flow
 - Internal pressures and temperatures
 - Proper functioning of gas flow controllers and switches

The RespirAct™ been used in about 500 cases at the Toronto Western Hospital in patients with significant impairment of the blood supply to the brain without undue effect or complication.

3. Neck Collar and Jugular compression

The physiological effect jugular venous compressions used in this study are minimal and the brief period of jugular occlusion is similar to the effects produced

by straining, coughing and heavy lifting. Neck collar will apply only minimal pressure on the neck, which is comparable to wearing a tight dress shirt and a tie.

4. Ultrasound

There are no risks with the use of ultrasound. Orbital ultrasound is routinely done in all patients coming for cataract and retinal surgery at Toronto Western Hospital. Around 30 patients undergo transorbital ultrasound every day at UHN. Ultrasound Gel can be cold on contact with skin.

Data collection

Data collected will include:

- Volunteer demographics
- Medical history
- Vital signs- Heart rate, non-invasive blood pressure and cardiac output, oxygen saturation, end-tidal Co₂ levels.
- Optic nerve sheath diameter at normocapnia, 2 levels of hypercapnia and hypocapnia.
- Internal jugular vein diameter and flow in supine and Siting position with and without the neck collar.
- The minimal pressure needed to occlude the IJV.

Data Analysis

A paired t test will be used to compare the following changes in ONSD

- Normocapnia (baseline Pco₂) to hypercapnia (baseline+10 mmHg)
- Normocapnia (baseline Pco₂) to Hypercapnia (baseline+15mmHg)
- Normocapnia (baseline Pco₂) to hypocapnia (baseline -10mmHg)
- Neck collar ON and OFF at each Co₂ levels.

Sample size

Since this is a preliminary study to evaluate the effect of hypercapnia and hypocapnia and IJ compression on ONSD, only a small sample is required. We intend to enroll 15 subjects in this initial phase. Given the fact that the CO₂ manipulation technique using the RespirAct™ is a new method developed at the University of Toronto and not yet widely available, the lack of information in the literature regarding its utilization for this purpose is obvious. We believe that this small sample will be sufficient to demonstrate the feasibility of the test and set the stage for larger studies.

Project Feasibility

We anticipate no difficulty in obtaining 15 volunteers to participate in this study. The RespirAct™ gas blender used for CO₂ manipulation has been installed at 10 sites including John's Hopkins, University of Colorado, Duke University, University of Nottingham, University of Montreal, University of Texas, and McGill University. The device has a proven track record with regard to clinical implementation.

Figures

[figure not shown]

Figure 1: Experimental protocol demonstrating target PetCO₂ levels with measurements being performed both while the venous compression collar is off and then subsequently applied.

[figure not shown]

Figure 2: An experiment of end-tidal CO₂ (PetCO₂) manipulation using MPET (RespirAct™). Please note the stable O₂ levels and the precision control of PetCO₂ levels.

[figure not shown]

Figure 3: Two-dimensional ocular sonography. A diagram showing the ultrasound probe, the ocular globe and the optic nerve with the optic nerve sheath diameter (ONSD) which was measured 3 mm behind the papilla using an electronic caliper (A X LONG measure) and an axis perpendicular to the optic nerve (B + LONG measure).

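### The sonographers are masked to each other but not, as far as stated, to collar state or CO2 level, so a bias both readers share could produce a change in ONSD

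*Combined protocol and SAP*

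**What the plan says.** - **Masking.** Under Ultrasound measurement of ONSD, two investigators are to examine "both eyes of all subjects independently without being aware of each other's study results". Each investigator scans each eye three times, and the mean is used.
- **Measurement.** The Figure 3 caption describes ONSD as "measured 3 mm behind the papilla using an electronic caliper".
- **Order.** Under Carbon dioxide Manipulation, the first raised CO2 level is "held for 5 minutes in order to complete ONSD measurements. The venous compression neck collar will then be applied", after which ONSD is measured again. The levels run +10, +15, then -10 mmHg from baseline, with a return to baseline between them, in the same order for every subject.
- **Collar.** The neck collar section describes an external elastic collar used at all four CO2 levels, and states that "ONSD measurements will be measures before and after the collar".
- **Hypothesis.** "Our hypothesis is that there will be a change in" ONSD with raised PCO2 and jugular occlusion.
- **Analysis.** Under Data Analysis: "A paired t test will be used to compare the following changes in ONSD". Three CO2 contrasts against normocapnia follow, then collar on against off at each CO2 level.

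The available text mentions no masking to condition, no concealed or sham collar, and no later reading of coded images. It also does not say who can see the RespirAct display or whether calipers are placed live.

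**The concern.** Masking the readers to each other makes their readings mutually independent, so it protects a comparison between readers. It does not protect a comparison between conditions, and between conditions is what every planned test compares. Placing a caliper on the sheath edge involves judgement. Both readers know that the study expects hypercapnia and venous occlusion to change ONSD, and the Background gives the mechanism as a rise in intracranial pressure. A reader who knows the collar is on, or that CO2 is raised, may place the calipers a little wider without intending to.

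A positive result would then have at least one rival explanation besides physiology. The study is described as preliminary, but it plans significance tests and is meant to prepare for larger studies. A biased estimate could be carried into them if it is used in their planning.

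**Working it through.** **1. Can a reader tell the condition?** The collar is on the neck of the person whose eyes are being scanned. Collar-off always precedes collar-on. The CO2 sequence is identical for everyone, so position in the session reveals the level even to someone who never sees the display. The 5-minute hold adds only that the scans are made within a known step. The visible collar and the fixed order are enough for live scanning.

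**2. Does averaging help?** Let each reading be the true value, plus a condition-dependent bias common to both readers, plus independent error with SD 1. With k readers, 2 eyes and 3 scans per eye, the difference between two conditions has:

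- mean = true change + b
- SD from reading error = √(2 / (6k))

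With true change 0 and b = 0.30, simulation (200,000 draws) agrees with the formula:

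| Readers k | Mean error | SD by formula | SD simulated |
|---|---|---|---|
| 1 | 0.30 | √(2/6) = 0.58 | 0.58 |
| 2 | 0.30 | √(2/12) = 0.41 | 0.41 |
| 10 | 0.30 | √(2/60) = 0.18 | 0.18 |

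The noise shrinks and the bias stays. Pairing within subject does not remove it either, because the bias differs between the two members of each pair.

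**3. What could it do to the planned test?** The plan gives no figure to reproduce: n = 15 is justified by feasibility, without alpha, SD, effect size or power. Assumptions for the illustration are two-sided alpha 0.05, true change zero, and shared bias d in units of the SD of the paired difference. The paired t statistic is then noncentral t with df = 14 and noncentrality d√15, where √15 = 3.873.

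Data Analysis lists 3 CO2 + 4 collar = 7 contrasts. The hypothesis covers the two hypercapnia and the four collar contrasts, so 6; it says nothing about hypocapnia. If the same bias acts on all six, the expected number falsely significant is 6p, which needs no independence between tests.

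| Bias d | d√15 | P(significant), p | 6p |
|---|---|---|---|
| 0 | 0 | 0.0500 | 0.30 |
| 0.10 | 0.387 | 0.0651 | 0.39 |
| 0.25 | 0.968 | 0.1474 | 0.88 |
| 0.50 | 1.936 | 0.4379 | 2.63 |
| 0.75 | 2.905 | 0.7707 | 4.62 |

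**4. Workload of masked reading.** Conditions: 4 CO2 levels x 2 collar states = 8. Frames: 2 investigators x 2 eyes x 3 scans x 8 conditions x 15 subjects = 1,440, or 720 per reader.

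- Reading at an assumed 30 s: 720 x 30 s = 6 h per reader (4 to 12 h at 20 to 60 s).
- Coding at an assumed 15 s: 1,440 x 15 s = 6 h (2 to 12 h at 5 to 30 s).
- Total: 2 x 6 + 6 = 18 person-hours (range 2 x 4 + 2 = 10 to 2 x 12 + 12 = 36).

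**The case against.** The strongest reply is that the point rests on silence. If frames are already stored and read later by masked readers, much of the problem disappears. That stands as a limit, and one sentence in the protocol would settle it. As written, the plan permits unmasked reading.

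The bias sizes are arbitrary, and the resulting 7% to 77% range is wide. This is also fair: the table shows how sensitive a 15-subject test is to a shared bias and is no evidence about how large that bias would be. It assumes zero true change, whereas the protocol expects a real one. If the effect is real, the harm is a distorted estimate (true change + b) instead of a false positive.

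The count of six is a reading of a one-sentence hypothesis that gives no direction and does not name the collar at normocapnia or hypocapnia. Counting only the two hypercapnia contrasts and the two collar contrasts at those levels gives 4p = 0.26, 0.59, 1.75 and 3.08, against 0.20 without bias. The per-contrast figures do not change.

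The remedy is partial. Choice of plane and frame stays unmasked, readers may recognise their own frames, and deferred reading may lose the chance to repeat an unmeasurable scan. Time drift and carry-over from the fixed order are separate rival explanations that masked reading leaves in place. All of this stands and belongs in the limitations. It does not justify leaving caliper placement, which can be masked, unmasked.

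**Conclusion.** The concern holds. The stated masking does not cover the comparisons being tested, and the procedures make it very likely that live readers know the condition. The only tested outcome is therefore open to a shared expectation bias that three scans per eye and two readers cannot average away.

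It is not shown that bias will occur, and its size cannot be derived from the documents. Under the stated assumptions, a shared bias of a quarter SD roughly triples the 5% error rate of a single contrast (to 14.7%), and half an SD raises it to 43.8%. This is an improvement the study should make. It does not invalidate the design.

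**What to change.** Amend Ultrasound measurement of ONSD as follows:

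1. During the session, the same two investigators save each frame without placing calipers, checking by eye that it is measurable so that a poor scan can still be repeated.
2. Staff who do not read scans code and shuffle the frames so that subject, CO2 level, collar state and time are hidden. The "Research coordinator for the study" named under Recruitment is a candidate, if available.
3. Each investigator later measures his or her own coded frames in random order across conditions, still unaware of the other's readings.
4. Data Analysis states that only these masked readings enter the paired t tests.
5. The protocol records as limitations that frame selection is unmasked and that order effects are not addressed by masked reading.

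Confirm beforehand that the ultrasound system can export frames free of calipers, time and identity marks; the documents do not say.

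**Cost.** No extra subjects, scans or readers, and no change to the CO2 or collar procedures. About 18 person-hours in total (10 to 36 over the assumed speeds), and results are available later. If masked offline reading is already intended, stating it is enough. If it is not feasible, the protocol should say that readers know the condition and report this as a limitation.

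### Does the silence on whether the ONSD paired t tests use one value per subject, per eye or per investigator call for a change to the plan?

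*Combined protocol and SAP*

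**What the plan says.** Under Ultrasound measurement of ONSD, the protocol states that "Two trained investigators will perform investigations on both eyes of all subjects independently without being aware of each other's study results". It continues: "Each eye will be examined 3 times by each investigator and the mean value of the ONSD will be used for further calculations". What the mean is taken over is not spelled out.

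Data Analysis states that "A paired t test will be used to compare the following changes in ONSD" and then lists three contrasts of a CO₂ level with normocapnia, plus collar on against collar off at each CO₂ level. The section on the neck collar names four such levels. Data Analysis gives no unit of analysis, degrees of freedom, significance level or method for clustered observations.

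Two other places bear on the unit. Sample size gives one number, in subjects: "We intend to enroll 15 subjects in this initial phase". Data collection lists "Optic nerve sheath diameter at normocapnia, 2 levels of hypercapnia and hypocapnia", with no index for eye or investigator.

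**The concern.** A paired t test assumes that the pairs are independent of one another. Pairing removes a subject's own baseline level, but not a response that is common to everything measured in that subject. Each CO₂ step and each collar application acts on the whole person, and both investigators scan the same eyes, so changes within a subject would be expected to move together. If eye-level or reader-level changes were entered as separate pairs, the standard error would then be too small and a change in ONSD would be declared too often.

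The wording leaves room for this. The sentence on averaging opens with each eye and each investigator, so a mean over the three repeats alone is a grammatical reading. All the planned tests would be affected, and they are the only analysis of the study's hypothesis. With so few subjects, the step from 15 to 30 or 60 pairs is large.

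**Working it through.** **Inputs from the protocol.** 15 subjects (Sample size); 2 eyes, 2 investigators and 3 repeats (Ultrasound measurement of ONSD); 3 CO₂ contrasts (Data Analysis); 4 CO₂ levels for the collar contrast (neck collar section). The sample size comes with no effect size, standard deviation, power or significance level, so there is no figure of the plan's own to reproduce.

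**Counts.**
- Scans per subject and condition: 2 × 2 × 3 = 12.
- Tests: 3 + 4 = 7.
- Mean over all 12 scans: 15 pairs.
- Mean per eye, or mean per subject and investigator: 15 × 2 = 30 pairs.
- Mean per eye and investigator: 15 × 2 × 2 = 60 pairs.

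**Assumptions not in the documents.** Two-sided 5% level, normally distributed changes, and a common correlation ρ between the m changes from one subject.

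**Approximation.** The true variance of the mean exceeds the naive one by the design effect 1 + (m − 1)ρ. The false positive rate is then roughly 2 × [1 − Φ(1.96 / √design effect)]. At ρ = 0.5:
- m = 2: design effect 1 + 0.5 = 1.5; 1.96 / √1.5 = 1.60; rate about 11.0%.
- m = 4: design effect 1 + 3 × 0.5 = 2.5; 1.96 / √2.5 = 1.24; rate about 21.5%.

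**Simulation of the naive t test with 15 subjects (100,000 null trials per case).**

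| Pairs | ρ = 0 | 0.1 | 0.2 | 0.5 | 0.8 |
|---|---|---|---|---|---|
| 15 | 5.0% | 5.1% | 5.0% | 5.0% | 4.9% |
| 30 | 5.0% | 6.2% | 7.3% | 11.1% | 15.0% |
| 60 | 5.0% | 8.5% | 12.2% | 22.1% | 30.4% |

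A separate simulation with 200,000 runs gave 11.2% and 22.0% at ρ = 0.5 for 30 and 60 pairs, in line with the table and the approximation. It also gave 4.0% for 30 pairs at ρ = −0.1, so the direction of the error depends on the sign of the correlation. If the two eyes' changes are uncorrelated but two investigators' changes on the same eye correlate 0.5, 60 pairs give 11.0%.

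**Which reading fits the text.** The averaging sentence speaks of one mean value. Sample size counts subjects and nothing else. Data collection indexes ONSD by CO₂ level only. All three fit one value per subject and condition. The last is weak evidence, because that list also omits collar state, although ONSD is measured with and without the collar. No passage calls for eyes or investigators to be entered as separate observations.

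**The case for a change.** The strongest case for a change is that these tests carry the whole inference, the text can be read more than one way, and silence would let someone choose the unit after seeing the data. The study is meant to prepare larger ones, and a standard error from 30 or 60 pooled pairs would overstate precision when they are planned. One sentence would settle it, at no cost in procedures.

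Most of this stands as a description of the gap. The unit is not stated, the arithmetic is sound, and positive correlation is the natural expectation. What does not follow is that the planned analysis is wrong. The sentence would only write down the reading that the text already favours: average the 12 scans to one value, with n equal to the subjects measured in both conditions (15 if all complete). Planned results would be the same. The choice would also be visible in any proper report, since the degrees of freedom would be 14, 29 or 59.

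It can also be argued that the duplicate readings should yield an estimate of observer agreement, because the background says "we need to determine how reliable the change in ONSD with controlled acute changes in intracranial pressure is". That sentence concerns how ONSD responds to changes in intracranial pressure, not agreement between readers, and agreement is not a stated objective. Such an analysis would be an extra and would alter none of the planned tests.

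**Conclusion.** The ambiguity is real, but it is a gap in detail and not a faulty rule. With one value per subject and condition, the natural reading, each test holds its assumed 5% level whatever the correlation. Rates of about 6 to 15% (30 pairs) and 9 to 30% (60 pairs) arise only if two conditions both hold: units below the subject are pooled without allowance for clustering, and changes within a subject correlate at 0.1 to 0.8. The plan does not adopt the first and gives no figure for the second. In a preliminary study of 15 subjects, whose protocol sets no significance level, no change to the plan is needed.
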